11.2 Informed Consent and Screening

11.2.1 Informed consent

If the patient appears to be a potential candidate for the study based upon existing information, a written informed consent will be obtained. Informed consent must be obtained prior to initiation of any clinical procedures that are performed solely for the purpose of determining eligibility for research, including withdrawal from medication. Patients who have completed or are in process of washout unrelated to this study may be considered for the study. When washout is done solely in anticipation of or in preparation for the research, it is part of the research and must be done after obtaining written consent.

Clinical investigators or designees will approach the patient to obtain a written informed consent. The background of the proposed study, the implant procedure, the follow-up schedule and all potential risks and benefits will be carefully explained to each patient. The clinical investigator or designee obtaining informed consent shall:

- Avoid any coercion of or undue influence of patients to participate,
- Not waive or appear to waive patient's legal rights,
- Use language that is non-technical and understandable to the patient, and
- Provide ample time for the patient to consider participation.

Each patient must sign and date the ICF approved by an appropriate IRB during an in-office visit. The original signed ICF will be placed in the study file, and a copy will be given to the subject.

Subjects will be re-consented in situations where changes were made to the study protocol or new information about the risks, possible benefits or alternative treatments have been identified. The sponsor and IRB will notify clinical investigators in the event re-consent is necessary. In this case, subjects must sign and date the amended ICF during their next in-office visit. The original will be placed in the study file, and a copy will be given to the subject.

11.2.2 Screening and baseline assessments

During the same in-office visit that written informed consent is obtained, each subject will be assigned a unique identifying code and undergo the following screening assessments to confirm their initial eligibility and obtain baseline values for RA disease activity assessments from which the primary and the key secondary efficacy endpoints will be assessed:

- Physical examination, including vital signs, height and weight

Note: If a subject has an active infection that does not clear before Implant Procedure, the subject is considered as a screen failure. The subject can be consented and screened following treatment and full recovery.

- Prior and current RA medications with detailed record of use of biologic, conventional and targeted synthetic DMARDs
- Medical history
- Female subjects of childbearing potential must confirm their nursing status, undergo pregnancy test, and confirm their birth control method(s) (see Section 12.1)
- RA disease activity assessments (see Section 12.2)
- Determining the need for washout from biologic or targeted synthetic DMARDs prior to Implant Procedure, depending on subject's current usage:
 - *Subjects in post-washout, requiring no further washout.* Subjects who stopped taking all biologic and targeted synthetic DMARDs for a period exceeding the required minimum washout period prior to Implant Procedure (see **Appendix A**) do not require further washout to qualify for the study.
 - *Subjects during washout, requiring completion of washout.* Subjects who stopped taking any biologic and targeted synthetic DMARDs within less than the required minimum washout period prior to Implant Procedure (see **Appendix A**) must complete washout during the screening period, prior to Implant Procedure to qualify for the study.
 - *Subjects in pre-washout, requiring washout.* Subjects who are currently taking any biologic and/or targeted synthetic DMARDs must stop taking them for the required minimum washout period during the screening period, prior to Implant Procedure (see **Appendix A**) to qualify for the study.

Note: If the required minimum washout period following informed consent exceeds 30 days for a given subject, this subject shall be considered screen failure without the possibility of reconsenting. This is because washout needs to be completed before Implant Procedure, which takes place within 30 days from the informed consent date.

- Energizer fit test
- Eligibility evaluation

The remaining screening assessments can be completed on the day of informed consent or shortly after, depending on scheduling abilities:

- Concomitant medications
- SF-36 and EQ-5D-5L questionnaires
- Blood collection for RF, ACPA, eGFR, CBC and biomarkers (see Section 12.3)

Note: eGFR must be confirmed prior to screening hand MRI

- Hand MRI (see Section 12.4)
- Reporting of any AEs

Pre-surgical clearance must be completed by the Co-PI Surgeon prior to the scheduled implant procedure and entails:

- Review of the screening data collected by the rheumatologist investigator
- 12-lead ECG and any additional tests required for surgical or anesthesia clearance per hospital's standard of care
- Standard cervical spine X-ray, including anterior-posterior, lateral full flexion and extension, and odontoid views to ensure there are no degenerative or inflammatory changes observed in the cervical spine that would predict significant risk for atlanto-axial subluxation during neck extension required for endotracheal intubation prior to implantation (Krause and Matteson 2014). Cervical spine disorders or instability that would preclude safe endotracheal anesthesia will render the subject ineligible. The radiology report shall be filed with the subject's source documentation.
- An assessment of eligibility based on criteria associated with comorbidities or current status of physical fitness that would make the subject medically unfit for the implant procedure.

Based on all screening assessments, Co-PI Rheumatologist conducts a final eligibility evaluation:

- A subject must meet all the inclusion criteria and none of the exclusion criteria to be eligible. A subject not meeting all inclusion criteria or meeting any exclusion criterion will be classified as a screen failure and exited from the study. The reason(s) for screen failure will be documented.

11.3 Enrollment and Implant Procedure

Subjects meeting final eligibility criteria and in whom the implant procedure is attempted are considered enrolled. The implant procedure shall occur within 30 days from informed consent. The implant procedure is an outpatient procedure taking place in an operating room under general anesthesia. The implant (MicroRegulator) and POD will be placed on the left cervical vagus nerve within the carotid sheath by surgeons trained and experienced in procedures involving implantation of VNS devices. The implant procedure must be performed according to SetPoint System Instructions for Use Surgeon Manual. All surgeons performing the implant procedure must have documented training prior to performing the first case. Upon completing the implant procedure, any AEs, device deficiencies and changes in concomitant medications will be recorded.

The pregnancy testing for female subjects of childbearing potential must be completed before initiation of the implant procedure (see Section **12.1**).

11.4 Post-Surgical Clearance

Subjects will undergo the following assessments within 14-21 days after Implant Procedure and prior to Day 0:

- Pregnancy test for female subjects with childbearing potential and confirmation of birth control method (see Section **12.1**)
- Surgical clearance, which includes:
 - Post-operative surgical evaluation of wound healing by the Co-PI Surgeon or designee at the surgical site, with special attention to wound infections
 - Final surgical clearance with an approval to initiate study treatment
- Reporting of any AEs, device deficiencies and change in concomitant medications

11.5 Day 0 Assessments, Randomization, and Initiation of Stimulation

11.5.1 Day 0 assessments

Subjects approved to initiate study treatment will undergo the following assessments within 14-21 days after Implant Procedure and before randomization:

- Collection of vital signs
- Pregnancy test for female subjects of childbearing potential and confirmation of birth control method (see Section **12.1**)
- RA disease activity assessments (see Section **12.2**)
- SF-36 and EQ-5D-5L questionnaires

- Blood collection for CBC and inflammatory biomarkers (see Section **12.3**)
- Reporting of any AEs, device deficiencies and change in concomitant medications.

11.5.2 Randomization

Upon completion of all Day 0 assessments, subjects will be randomly assigned in a 1:1 ratio to either treatment or control group using an interactive response technology (IRT) system. Subjects assigned to the treatment group will receive active stimulation for 1 min once per day, and those assigned to the control group will receive sham (non-active) stimulation for 1 min once per day. Subjects and study staff will be kept blinded (see Section **18.3**).

For subjects assigned to the control group, their MicroRegulator will be registered to a prescription rule to deliver a sham stimulation, regardless of the setting assigned. The registration is performed by unblinded technicians at SetPoint Medical who have exclusive access to the subject's treatment assignment. The prescription rule is written in the SetPoint Medical cloud and is received by the site's Prescription Pad when connected to Wi-Fi and then applied to MicroRegulator via Energizer. The prescription rule is not visible to the site personnel to ensure they remain blinded to treatment assignment.

11.5.3 Initiation of stimulation

After randomization, all subjects (treatment and control) will undergo device check, dose titration and training on the use of Energizer. The device check and dose titration must be performed by a study staff member at the rheumatology site who has been delegated as the site's device programmer and completed the required programming training. Both delegation and training must be documented in the appropriate forms.

11.5.4 Device check and dose titration/adjustment

Device check

The research coordinator or designee delegated to perform device programming will first perform a device check and then dose titration while subjects are wearing their Energizer. The device check entails connecting Prescription Pad to the site's WiFi and establishing the Bluetooth connection between Prescription Pad and the subject's Energizer. Once Prescription Pad is connected to Energizer, and Energizer is connected to MicroRegulator, Prescription Pad will display the following information:

- Current prescription settings (i.e., strength of stimulation)
- Total number of doses delivered at current setting
- Number of doses missed
- MicroRegulator battery level
- MicroRegulator impedance

Note: If a charge level of less than 75% is observed, the subject will be counseled on the importance of charging their implant on a weekly basis. Failure to charge the MicroRegulator for an extended period may result in a complete discharge of its battery. Once fully discharged, the battery cannot be recharged, and automatic delivery of stimulation will no longer occur. In this case, the MicroRegulator must be decommissioned (permanently turned off) and the subject must return all external equipment (Energizer and Wireless Charger) (see Section 11.9).

Dose titration

Dose titration entails an iterative procedure during which short test stimulations will be delivered and assessed by subject for tolerability. If tolerated, the stimulation strength will be incremented and assessed again. This will be repeated to the maximum level tolerated or to the maximum allowable current level specified for the visit, whichever comes first. Once the desired stimulation strength is determined or achieved, the subject's MicroRegulator will be set to deliver stimulation at that dose for 1 minute per day. The device programmer will follow the same schedule and procedure for all subjects (treatment and control). Subjects, regardless of treatment assignment, should not be told or shown what their stimulation strength is set to.

The titration visits occur at timepoints specified in Section 6. Titration visits will be short and consist of a device check and dose titration, as described above. No study required RA assessments will be performed during those visits. All AEs, device deficiencies and changes in concomitant medications will be recorded. Female subjects with childbearing potential will undergo a pregnancy test and confirmation of birth control method per Section 12.1.

Dose adjustment

If there is a need to change the stimulation strength, a dose adjustment may be performed. The reason for dose adjustment must be documented. Reasons include an AE such as subject side effect (see Section 16.2). The process for adjusting the stimulation strength is similar to that for dose titration and consists of short test stimulations that are assessed by subject for tolerability. If tolerated, the stimulation strength will be incremented and assessed again. This will be repeated to the maximum level tolerated. Once the desired stimulation strength is determined or achieved, the subject's MicroRegulator will be set to deliver stimulation at that dose for 1 minute per day.

11.6 Follow-up

The follow-up period begins immediately post-randomization and initiation of stimulation. Each subject will return for 6 follow-up visits between Day 0 and Week 12, and 24 follow-up visits in the open-label, long-term follow-up period, starting after Week 12 assessments and continuing through Week 264 (end of study). Visits must occur within specified windows from Day 0 as detailed in Schedule of Assessments (see Section 6).

The protocol-required follow-up assessments are described in the following sections.

11.6.1 Follow-up through Week 12

The protocol-required follow-up assessments at Week 4, 8 and 12 include the following and should be performed in the order specified prior to the device check and any dose adjustment:

- Subject's, Joint Evaluator's and Co-PI Rheumatologist blinding assessment (Week 4 and 12)
- Collection of vital signs (Week 12)
- 12-lead ECG (Week 12)
- Pregnancy test for female subjects with childbearing potential and confirmation of birth control method (see Section 12.1)
- RA disease activity assessments (see Section 12.2)
- SF-36 and EQ-5D-5L questionnaires
- Blood collection for CBC and inflammatory biomarkers (see Section 12.3)
- Reporting of any AEs, device deficiencies and change in concomitant medications
- Suspending therapy before the hand MRI (Week 12; see Section 11.8)
- Hand MRI (Week 12; see Section 12.4)
- Review of clinical outcomes and discussion of treatment options for continuation in the long-term follow-up period of the study (after completing assessments at Week 12). The Co-PI Rheumatologist will review with the subject their clinical outcomes and determine which option is in the subject's best interest. The Co-PI Rheumatologist and the subject are blinded to initial treatment assignment in making this decision. The option chosen will be recorded on the follow-up visit CRF and entered into EDC. Options include:
 - Receive active stimulation
 - Receive additional RA treatment with active stimulation (see Section 14.5)
 - Receive additional RA treatment without active stimulation (i.e., stimulation is suspended, see Section 11.8) with a possibility to receive active stimulation at a later time
 - Permanently turn off (decommission) the study implant (see Section 11.9)
 - Undergo an explant procedure to surgically remove the implant (see Section 11.10)
- Re-registration of Microregulator following MRI at Week 12. Cross-over of the control group to active stimulation by updating the prescription rule to deliver active stimulation. The prescription rule for treatment subjects will remain the same, delivering active stimulation. Re-registration will be performed by unblinded technicians at SetPoint Medical. The blind for all study roles that are blinded will be maintained (see Section 18.3).
- Device check and dose titration following MicroRegulator re-registration at Week 12, depending on the option chosen for long-term follow-up.

11.6.2 Open-label, long-term follow-up through Week 264

Protocol-required follow-up assessments at Week 24 through Week 264 are detailed below and in Schedule of Assessments (see Section 6) and should be performed in the order specified prior to the device check and any dose adjustment:

- Collection of vital signs
- 12-lead ECG (Week 24, 48, 96, 144, 192)
- Pregnancy test for female subjects with childbearing potential and confirmation of birth control method (see Section 12.1)
- RA disease activity assessments (see Section 12.2)
- SF-36 and EQ-5D-5L questionnaires (Week 24, 48, 96, 144, 192)
- Satisfaction Questionnaire (Week 24)
- Blood collection for CBC (see Section 12.3)
- Blood collection for inflammatory biomarkers (Week 24) (see Section 12.3)
- Reporting of any AEs, device deficiencies and change in concomitant medications, including the need, timing and type of additional RA treatment
- Suspending therapy before the hand MRI and resuming therapy afterwards (Week 24; see Section 11.8)
- Hand MRI (Week 24; see Section 12.4)

At Week 264, once all assessments are completed, every subject's MicroRegulator must be decommissioned (see Section 11.9).

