12.2.5 EGA

After performing joint assessments, the same Joint Evaluator will conduct a global assessment of the subject's RA activity using a paper form. Each subject should be assessed by the same Joint Evaluator throughout their participation in the study. The subject's Joint Evaluator *must* be the same at Screening and Week 12. The Joint Evaluator must complete their assessments without knowledge of SGA.

12.2.6 hsCRP

Blood samples for hsCRP will be collected using sampling kits and shipped at room temperature to a central laboratory for analysis through Week 192 (see Section 12.3). Serum concentration of hsCRP (mg/L) will be determined by immunoturbidimetric assay. Blood samples for hsCRP will be analyzed locally from Week 204 through Week 264.

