8.7 Blinding Assessment

The effectiveness of blinding of subjects, joint evaluators and Co-PI Rheumatologists will be evaluated at Week 4 and Week 12 using a blinding questionnaire with the following questions:

- I strongly believe I am [or subject is] in the treatment group and receiving therapeutic stimulation
- I somewhat believe I am [or subject is] in the treatment group and receiving therapeutic stimulation
- I somewhat believe I am [or subject is] in the control group and receiving non-therapeutic stimulation
- I strongly believe I am [or subject is] in the control group and receiving non-therapeutic stimulation
- I don't know which group I am [or subject is] and which stimulation I am [or subject is] receiving

The statistical test will be Bang's blinding index (BI) and its associated 95% confidence interval (Bang 2010). The BI will be calculated for both the ITT and PTE populations.

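### Protocol 11.6.1 places the blinding questionnaire ahead of the RA ratings at Weeks 4 and 12, which may prime the rated components of ACR20

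*Protocol*

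**What the plan says.** Protocol 11.6.1 states that the Week 4, 8 and 12 assessments "include the following and should be performed in the order specified prior to the device check and any dose adjustment". The first item is "Subject's, Joint Evaluator's and Co-PI Rheumatologist blinding assessment (Week 4 and 12"). The next items are "Collection of vital signs (Week 12"), "12-lead ECG (Week 12") and "Pregnancy test for female subjects with childbearing potential and confirmation of birth control method (see Section 12.1"). The fifth item is "RA disease activity assessments (see Section 12.2").

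Protocol 12.2 fixes the order inside the RA assessments (HAQ-DI, SGA, pain, TJC28, SJC28, EGA, hsCRP) and does not mention the blinding questionnaire. Section 8.7 of the SAP for the interim and primary analyses (CLP-004) gives the response set: strong or moderate belief that the subject is "in the treatment group and receiving therapeutic stimulation", the same two grades for control, or don't know. It does not say when in the visit the form is completed.

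On keeping ratings independent, Protocol 12.2.5 says "The Joint Evaluator must complete their assessments without knowledge of SGA", and Protocol 12.2.2 has subjects rate independently of the evaluator. Neither section deals with a rater's own guess. No reason is given for the order in 11.6.1.

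**The concern.** The people who answer the questionnaire include those who produce the primary endpoint. Asking a rater which arm the subject is in, shortly before that rater scores pain, function, joints or global activity, brings the belief to mind at the moment of scoring. The mock listings for the blinding assessments in CLP-004 Appendix C also carry a column for the reason behind the answer, so the form appears to ask for more than a tick.

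Week 12 is the visit on which ACR20 and all four key secondary endpoints are determined. A bias that arises when the rating is made is not removed by randomisation. Bang's index may reveal that guesses track assignment, but it corrects nothing, and none of the ACR20 sensitivity analyses in CLP-004 8.3.4 uses the recorded guess.

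**Working it through.** **1. Position in the visit (Protocol 11.6.1).**

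| Order | Item | Week 4 | Week 12 |
|---|---|---|---|
| 1 | Blinding questionnaire | yes | yes |
| 2 | Vital signs | no | yes |
| 3 | 12-lead ECG | no | yes |
| 4 | Pregnancy test | if applicable | if applicable |
| 5 | RA assessments | yes | yes |

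At Week 12, two or three procedures separate the question from the ratings. At Week 4, at most one does.

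**2. Who rates what (CLP-004 8.3.1; Protocol 12.2).** The subject rates pain, SGA and HAQ-DI. The Joint Evaluator rates TJC28, SJC28 and EGA. Only hsCRP is a laboratory value, so 3 + 3 = 6 of 7 components come from people who have just been asked. The subject's three items could meet the three-of-five requirement alone. They cannot produce a response alone, because both evaluator-scored joint counts must also improve by 20%.

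**3. When the order biases the comparison.** Let a and s be the shares in an arm who believe active and sham, with don't know as the reference. Let δa and δs be the change in response probability caused by asking *before* rather than after the ratings, in each belief group, assumed to depend on the belief and not on the arm. Then

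spurious difference = δa × (a in treatment − a in control) + δs × (s in treatment − s in control).

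If belief shares are equal across arms, both brackets are zero and priming only adds noise. If they differ, the result need not be zero. The documents give no value for a, s, δa or δs, so the expression cannot be evaluated.

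**4. Are unequal beliefs plausible?** For subjects, yes. Titration raises the current to the highest tolerated or allowed level (Protocol 11.5.4), while a control device delivers sham whatever the setting (11.5.2). Protocol 16.2 lists cough, hoarseness and throat pain with marketed VNS devices, generally only while stimulation is on. For the Joint Evaluator this argument does not apply: the evaluator does not feel stimulation, and programming belongs to the Research Coordinator or designee (Protocol 4 and 11.5.4).

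**5. How sensitive the trial is to a small bias from any source.** This step says nothing about the size of priming. Inputs: 125 per arm, 30% control response, one-sided alpha 0.025, and a Stage 1 stop if the difference in 30 versus 30 subjects is below 10 points (fewer than 3 responders). The test is the pooled chi-square, z = (pT − pC) / √[p̄(1 − p̄) × 2/125], with success if z > 1.96, in 1,000,000 simulated trials per case.

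The plan's power reproduces: 0.9585 against the stated 0.959 (60% vs 30%), and 0.773 against 0.773 (50% vs 30%). With no true effect and an *assumed* spurious difference:

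| Assumed spurious difference (points) | Success, with stop | Success, without stop |
|---|---|---|
| 0 | 0.017 | 0.025 |
| 1 | 0.026 | 0.037 |
| 2 | 0.037 | 0.053 |
| 3 | 0.052 | 0.074 |
| 5 | 0.096 | 0.133 |

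The 0 and 5 rows with the stop match Table 2 of CLP-004 (0.017 and 0.096).

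**The case against.** The best defence is that this is a trade-off. Asking first keeps the guess clear of that visit's pain, function and joint findings. Asked afterwards, a correct guess may reflect perceived benefit rather than unblinding, which makes Bang's index harder to read. That stands, but the index is listed among the exploratory endpoints in CLP-004 Table 4, while ACR20 decides the trial.

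It also stands that the order is the same in both arms, and that the case for beliefs associated with assignment is made for subjects and not shown for the evaluator.

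Stronger readings are tempting, and the documents do not support them:

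- *Raters are made to guess.* The form offers a don't-know answer, and the protocol recommends the order rather than mandating it.
- *The question comes immediately before the ratings.* At Week 12, vital signs and an ECG are listed in between.
- *The bias can be sized* by multiplying an assumed gap in belief by an assumed share of responses that flip, then set against the smallest significant difference of 11.2 to 12.8 points in CLP-004 3.4. Such a product measures the effect of holding a belief. A subject who feels stimulation holds that belief whether or not a form asks, and moving the form would not remove it. Only the extra effect of asking first is at issue.
- *The rule on SGA contradicts the visit order.* It keeps the evaluator's scores independent of the subject's score and does not address when beliefs are elicited.

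**Conclusion.** The point holds as a possible, avoidable source of priming. The prescribed order puts the blinding question before the RA ratings at Weeks 4 and 12, no other section reverses or justifies it, and the subject and Joint Evaluator rate six of the seven ACR20 components.

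Bias between arms rests on two assumptions: that asking first shifts ratings beyond what the belief alone would do, and that beliefs are associated with assignment. The second is plausible for subjects; neither can be confirmed from the documents. If the second fails, the cost is noise. No size can be given. The table shows only that a bias of a few points, if one existed, would matter. The change is worth making because it is cheap and protects the primary endpoint, not because harm has been shown.

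**What to change.** In Protocol 11.6.1, move the blinding assessment to directly after the RA disease activity assessments and SF-36/EQ-5D-5L, and before the review of clinical outcomes, re-registration and device check. Apply this at both Week 4 and Week 12, change the source worksheet to match, and state the position in CLP-004 8.7.

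Costs and limits:

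- The guess may be more influenced by that visit's ratings, which affects only the blinding index.
- The Week 4 question still precedes the Week 12 ratings by about eight weeks (84 − 28 = 56 days), so prompting is reduced rather than abolished.
- Subjects already assessed, including Stage 1, keep the existing order, and the primary analysis pools both stages. Record which order applied to each subject.

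For subjects already assessed, disclose the order used in the study report. The documents do not say whether any Week 12 visits remain; if none do, disclosure is the only part that still applies.
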